### 9.9.2 Safety Analysis

The primary safety analysis will summarize the safety data for participants during the treatment period (IV and oral treatment phases) plus 14 days of follow-up.

The APaT population is expected to include approximately 30 participants. The estimate of and the upper bound of the 95% CI for the underlying percentage of participants with a specific AE, given various hypothetical observed number of participants with that specific

AE within the study, are provided in Table 10. These calculations are based on the exact binomial method proposed by Clopper and Pearson.

Ν	Hypothetical Number of Participants with AE	Estimate of Incidence	95% CI Upper Limit a
	0	0.0%	9.5%
	2	6.7%	22.1%
30	5	16.7%	34.7%
	10	33.3%	52.8%
	15	50.0%	68.7%

Table 10Estimate of Incidence of a Specific AE and Upper Limit of 95% CI Based on aHypothetical Number of Participants with that Specific AE

Abbreviations: AE=adverse event; CI = confidence interval.

a Based on the 2-sided exact 95% confidence interval (CI) on a binomial proportion [Clopper, C. J. and Pearson, E. S. 1934].

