### 9.6.3 Safety Analysis

Safety and tolerability will be assessed by clinical review of all relevant parameters including AEs and laboratory parameters. The primary safety analysis will summarize the safety data for participants during the treatment period (IV and oral treatment phases) plus 14 days of

MK-5592-104-04 FINAL PROTOCOL

78

follow-up. Additional safety summaries will be presented in aggregate and by age cohort. No further summary breakdowns by formulations will be performed due to small sample sizes and potential of switching participants back and forth among formulations.

In this descriptive study, the primary safety endpoint of the proportion of participants with drug-related AEs will be provided along with the corresponding 95% CI. The 95% CIs for the safety parameters will be estimated using the Clopper-Pearson method, which is a conservative exact method of providing CIs in this single-arm study.

All other safety parameters will be summarized using descriptive statistics. These include the proportion of participants with the following safety parameters: (1) at least 1 AE; (2) an SAE; (3) a serious and drug-related AE; (4) an AE leading to discontinuation; (5) specific AEs by System Organ Class; and (6) predefined limits of change in specific laboratory parameters. In addition, vital signs, 12-lead ECGs, and standard laboratory safety tests at time points specified in the SoA will be summarized as change from baseline.

The analysis strategy for the safety parameters is summarized in Table 8.

Safety Endpoint	95% CI	Descriptive Statistics			
Any AE		X			
Any SAE		Х			
Any Drug-Related AE	Х	X			
Any Serious and Drug-Related AE		X			
Discontinuation due to AE		X			
Specific AEs, SOCs or PDLCs		X			
Change from Baseline Results (laboratory, ECGs, vital signs)		Х			
Abbreviations: AE=adverse event; CI=confidence interval; ECG = electrocardiogram; PDLC=Predefined Limit of Change; SAE=serious adverse event; SOC=System Organ Class; X=results will be provided.					

Table 8Analysis Strategy for Safety Parameters

Missing values will be handled using the Data-As-Observed approach; that is, any missing values will be excluded from the analysis.

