# 9.9 Sample Size and Power Calculations

# 9.9.1 Efficacy Analysis

The sample size was chosen based on clinical considerations, not statistical ones. However, of interest is the precision of the estimates of efficacy. The width of the 95% CI for the global clinical response rate will depend on the size of the population and the number of participants who achieve a favorable clinical response. In a study completed in 2019 (P069) in 575 adults and adolescents to study efficacy and safety of POS versus VOR for the treatment of invasive aspergillosis, the favorable global clinical response rates at Week 6 and Week 12 for the participants on POS were 45% and 42%, respectively [Maertens, J. A., et al 2021].

Table 9 summarizes the observed global clinical response rate and the corresponding 95% CI for a variety of observed response rates for a population of 15 participants (the overall evaluable population).

Number of Participants in Population	Number Achieving Clinical Response	Observed Global Clinical Response	95% Confidence Interval a	
	9	60.0%	[32.3, 83.7]	
15	6	40.0%	[16.3, 67.7]	
	3	20.0%	[4.3, 48.1]	
a Confidence intervals are based on the Clopper-Pearson method [Clopper, C. J. and Pearson, E. S. 1934].				

Table 9Summary of Potential Observed Global Clinical Response Rates and95% Confidence Intervals

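### Table 10 prints 9.5% as the upper 95% limit for 0 of 30 participants; the two-sided exact method it cites gives 11.6%

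*Combined protocol and SAP*

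**What the plan says.** Section 9.9.2 sets out what about 30 participants can show on safety: "The APaT population is expected to include approximately 30 participants". Table 10 lists, for N = 30, five hypothetical counts of participants with a specific AE, the observed incidence, and the upper limit of the 95% confidence interval:

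| Events | Incidence | Upper limit as printed |
|---|---|---|
| 0 | 0.0% | 9.5% |
| 2 | 6.7% | 22.1% |
| 5 | 16.7% | 34.7% |
| 10 | 33.3% | 52.8% |
| 15 | 50.0% | 68.7% |

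The method is stated twice. The text says "These calculations are based on the exact binomial method proposed by Clopper and Pearson". The footnote, attached to the column heading and so covering every row, says "Based on the 2-sided exact 95% confidence interval (CI) on a binomial proportion". Section 9.6.3 plans the same method for the analysis: "The 95% CIs for the safety parameters will be estimated using the Clopper-Pearson method". No separate convention for zero events is given in either section.

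**The concern.** When no events are seen, the exact upper limit has a closed form, so the first row can be checked by hand. It comes out higher than the printed value, and the printed value is the familiar one-sided bound. If so, the column holds limits at two confidence levels: 97.5% in the upper tail for four rows and 95% for the first.

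The zero-event row answers a natural question in a small paediatric safety study: how common could an event be if none of the children has it? Safety is the primary objective (Section 3), and Table 10 is the plan's only statement of safety precision. A limit that is too low there claims a tighter exclusion than the stated method supports, and the row cannot be compared directly with those beneath it.

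**Working it through.** **Inputs.** N = 30 (Section 9.9.2 and Table 10). Confidence level 95%, two-sided, so 0.025 in each tail (Table 10 footnote). Method: exact binomial, Clopper-Pearson (Section 9.9.2 text).

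**Formula.** For x events in n participants, the Clopper-Pearson upper limit is the (1 − a) quantile of a Beta(x + 1, n − x) distribution, with a = 0.025 for a two-sided 95% interval and a = 0.05 for a one-sided 95% bound. For x = 0 it reduces to 1 − a^(1/n).

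**Reproducing the table.**

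| Events of 30 | Printed | Two-sided (a = 0.025) | One-sided (a = 0.05) |
|---|---|---|---|
| 0 | 9.5% | 11.57% | 9.50% |
| 2 | 22.1% | 22.07% | 19.53% |
| 5 | 34.7% | 34.72% | 31.90% |
| 10 | 52.8% | 52.81% | 49.94% |
| 15 | 68.7% | 68.70% | 66.11% |

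Four rows match the two-sided column and only that column. The zero row matches the one-sided column and only that column.

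**The zero row by hand.**

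- Two-sided: 1 − 0.025^(1/30) = 1 − 0.8843 = 0.1157, or 11.6%.
- One-sided: 1 − 0.05^(1/30) = 1 − 0.9050 = 0.0950, or 9.5%.

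**Check from the other direction.** At a true rate of 9.5%, the chance of no events in 30 is (1 − 0.095)^30 = 0.050. At 11.57% it is 0.025, which is what a two-sided 95% limit requires. Read as the upper end of a symmetric two-sided interval, 9.5% has confidence 1 − 2 × 0.050 = about 90%.

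**Size.** 11.57 − 9.50 = 2.07 percentage points, and 2.07 / 11.57 = 18% of the correct value. For 0/n, the two-sided limit is 9.74% at n = 36 and 9.49% at n = 37, so 37 participants would be needed to print 9.5%.

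**Other methods for 0/30.** Wilson gives 11.35%, Agresti-Coull 13.47%, equal-tailed Jeffreys 7.97%, and the rule of three 10.0%. Mid-p gives 9.50%, because with no events its condition 0.5 × (1 − p)^30 = 0.025 is the same equation as the one-sided exact bound.

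**Convention elsewhere.** The three Table 9 intervals (n = 15) also reproduce as two-sided Clopper-Pearson: 9/15 gives 32.29% to 83.66%, 6/15 gives 16.34% to 67.71%, and 3/15 gives 4.33% to 48.09%. The 0/30 cell is the only exception in the two tables.

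**The case against.** The arithmetic is not in dispute; the case on the other side concerns origin and weight.

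First, 9.5% may be deliberate. With no events the lower limit is fixed at zero, and some analysts then put the whole 5% in the upper tail. On that reading 9.5% is a valid 95% upper bound with the wrong label. Mid-p would give the same number. The documents do not say which, if either, was meant. This stands as a possible explanation, but it does not rescue the table: the footnote says two-sided and exact for the whole column, so either the number or its label is wrong.

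Second, nothing in the plan turns on this cell. There are no hypotheses, and Section 9.9.1 says "The sample size was chosen based on clinical considerations, not statistical ones". No interim analysis is prespecified, and the early-termination criterion in Section 4.4.1 has no numerical AE threshold. This stands.

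Third, a clash with the eventual results is unlikely. Table 8 assigns a 95% interval only to any drug-related AE; specific AEs, the subject of Table 10, get descriptive statistics alone. A mismatch would therefore need 0 of 30 children with any drug-related AE. Section 2.1 reports 16 of 31 (52%) for treatment-related AEs in a paediatric trial of another azole, which is only indicative but makes a count of zero look improbable. This also stands, and it limits the consequence to how the planning table is read.

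An expected population of only approximately 30 does not explain the gap: the table prints N = 30, and 37 would be needed.

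**Conclusion.** The 0/30 entry in Table 10 is wrong under the table's own stated method. It should read 11.6% rather than 9.5%, an understatement of 2.1 percentage points, or about 18% of the correct limit, in the direction that flatters what zero events can rule out. The conclusion rests only on N = 30 and the two-sided exact 95% Clopper-Pearson interval, both stated in Section 9.9.2. A rounding difference cannot produce the gap, and the agreement of the other four rows and of Table 9 shows that two-sided limits are the convention in use.

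The error is confined to one cell. It does not affect the sample size, endpoints, populations or planned analyses. It merits correction because it misstates the precision available for the primary objective and is easily checked by any reader.

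**What to change.** In Table 10, replace 9.5% with 11.6% in the zero-event row. Leave the other four rows, the footnote and the text of Section 9.9.2 as they are. The cost is one table cell and a slightly less favourable figure; there is no effect on conduct or analysis.

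If the one-sided value was intended, keeping 9.5% with its own footnote marking that row as a one-sided 95% bound would also remove the contradiction. Printing 11.6% is preferable because it keeps the column on one convention and lets the rows be compared.

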# 9.10 Subgroup Analyses

No subgroup analyses are planned in this study.

### 9.11 Compliance (Medication Adherence)

The date and time of administration of each dose of POS, whether IV or oral (tablet or PFS) formulation, will be collected via eCRF to assess compliance for each participant. For the IV formulation, length of infusion will also be recorded.

For each participant who completes or who discontinues from the study or discontinues from study treatment, percent compliance will be calculated using the following formula:

 $\label{eq:percent compliance} Percent \ Compliance \ = \ \frac{\text{Number of Days on Therapy}}{\text{Number of Days Should be on Therapy}} \times \ 100.$ 

The numerator, ie, 'Number of Days on Therapy', is defined as the total number of days on which a participant receives actual treatment (ie, at least 1 infusion, sachet [containing PFS] or tablet of POS). The denominator, ie, 'Number of Days Should be on Therapy', is defined as the total number of days from the date of the first dose through the date of the last dose of study treatment.

Summary statistics such as mean and range of percent compliance for POS study treatment (IV, tablet, and PFS formulations) will be provided by age cohort and overall for the APaT population.

MK-5592-104-04 FINAL PROTOCOL

81

## 9.12 Extent of Exposure

The extent of exposure to study treatment will be evaluated by summary statistics (N, mean, median, standard deviation) and frequency for the "Number of Days on Therapy" by age cohort and overall.

## 10 SUPPORTING DOCUMENTATION AND OPERATIONAL CONSIDERATIONS

### 10.1 Appendix 1: Regulatory, Ethical, and Study Oversight Considerations

#### **10.1.1** Code of Conduct for Clinical Trials

#### Merck Sharp & Dohme LLC, Rahway, NJ, USA (MSD)

#### **Code of Conduct for Interventional Clinical Trials**

#### I. Introduction

#### A. Purpose

MSD, through its subsidiaries, conducts clinical trials worldwide to evaluate the safety and effectiveness of our products. As such, we are committed to designing, implementing, conducting, analyzing, and reporting these trials in compliance with the highest ethical and scientific standards. Protection of participants in clinical trials is the overriding concern in the design and conduct of clinical trials. In all cases, MSD clinical trials will be conducted in compliance with local and/or national regulations (including all applicable data protection regulations), and International Council for Harmonisation Good Clinical Practice (ICH-GCP), and also in accordance with the ethical principles that have their origin in the Declaration of Helsinki.

#### B. Scope

Highest ethical and scientific standards shall be endorsed for all clinical interventional investigations sponsored by MSD irrespective of the party (parties) employed for their execution (e.g., contract research organizations, collaborative research efforts). This Code is not intended to apply to trials that are observational in nature, or which are retrospective. Further, this Code does not apply to investigator-initiated trials, which are not under the full control of MSD.

#### II. Scientific Issues

#### A. Trial Conduct

#### 1. Trial Design

Except for pilot or estimation trials, clinical trial protocols will be hypothesis-driven to assess safety, efficacy and/or pharmacokinetic or pharmacodynamic indices of MSD or comparator products. Alternatively, MSD may conduct outcomes research trials, trials to assess or validate various endpoint measures, or trials to determine patient preferences, etc.

The design (i.e., participant population, duration, statistical power) must be adequate to address the specific purpose of the trial. Participants must meet protocol entry criteria to be enrolled in the trial.

#### 2. Site Selection

MSD selects investigative sites based on medical expertise, access to appropriate participants, adequacy of facilities and staff, previous performance in clinical trials, as well as budgetary considerations. Prior to trial initiation, sites are evaluated by MSD personnel (or individuals acting on behalf of MSD) to assess the ability to successfully conduct the trial.

#### 3. Site Monitoring/Scientific Integrity

Investigative trial sites are monitored to assess compliance with the trial protocol and Good Clinical Practice (GCP). MSD reviews clinical data for accuracy, completeness, and consistency. Data are verified versus source documentation according to standard operating procedures. Per MSD policies and procedures, if fraud,

scientific/research misconduct or serious GCP-non-compliance is suspected, the issues are investigated. When necessary, the clinical site will be closed, the responsible regulatory authorities and ethics review committees notified.

#### **B.** Publication and Authorship

Regardless of trial outcome, MSD commits to publish the primary and secondary results of its registered trials of marketed products in which treatment is assigned, according to the pre-specified plans for data analysis. To the extent scientifically appropriate, MSD seeks to publish the results of other analyses it conducts that are important to patients, physicians, and payers. Some early phase or pilot trials are intended to be hypothesis-generating rather than hypothesis testing; in such cases, publication of results may not be appropriate since the trial may be underpowered and the analyses complicated by statistical issues such as multiplicity.

MSD's policy on authorship is consistent with the recommendations published by the International Committee of Medical Journal Editors (ICMJE). In summary, authorship should reflect significant contribution to the design and conduct of the trial, performance or interpretation of the analysis, and/or writing of the manuscript. All named authors must be able to defend the trial results and conclusions. MSD funding of a trial will be acknowledged in publications.

#### III. Participant Protection

#### A. Regulatory Authority and Ethics Committee Review (Institutional Review Board [IRB]/Independent Ethics Committee [IEC])

All protocols and protocol amendments will be submitted by MSD for regulatory authority acceptance/authorization prior to implementation of the trial or amendment, in compliance with local and/or national regulations.

The protocol, protocol amendment(s), informed consent form, investigator's brochure, and other relevant trial documents must be reviewed and approved by an IRB/IEC before being implemented at each site, in compliance with local and/or national regulations. Changes to the protocol that are required urgently to eliminate an immediate hazard and to protect participant safety may be enacted in anticipation of ethics committee approval. MSD will inform regulatory authorities of such new measures to protect participant safety, in compliance with local and/or national regulations.

#### B. Safety

The guiding principle in decision-making in clinical trials is that participant welfare is of primary importance. Potential participants will be informed of the risks and benefits of, as well as alternatives to, trial participation. At a minimum, trial designs will take into account the local standard of care.

All participation in MSD clinical trials is voluntary. Participants enter the trial only after informed consent is obtained. Participants may withdraw from an MSD trial at any time, without any influence on their access to, or receipt of, medical care that may otherwise be available to them.

#### C. Confidentiality

MSD is committed to safeguarding participant confidentiality, to the greatest extent possible. Unless required by law, only the investigator, Sponsor (or individuals acting on behalf of MSD), ethics committee, and/or regulatory authorities will have access to confidential medical records that might identify the participant by name.

#### D. Genomic Research

Genomic research will only be conducted in accordance with a protocol and informed consent authorized by an ethics committee.

#### IV. Financial Considerations

#### A. Payments to Investigators

Clinical trials are time- and labor-intensive. It is MSD's policy to compensate investigators (or the sponsoring institution) in a fair manner for the work performed in support of MSD trials. MSD does not pay incentives to enroll participants in its trials. However, when enrollment is particularly challenging, additional payments may be made to compensate for the time spent in extra recruiting efforts.

MSD does not pay for participant referrals. However, MSD may compensate referring physicians for time spent on chart review and medical evaluation to identify potentially eligible participants.

#### B. Clinical Research Funding

Informed consent forms will disclose that the trial is sponsored by MSD, and that the investigator or sponsoring institution is being paid or provided a grant for performing the trial. However, the local ethics committee may wish to alter the wording of the disclosure statement to be consistent with financial practices at that institution. As noted above, all publications resulting from MSD trials will indicate MSD as a source of funding.

#### C. Funding for Travel and Other Requests

Funding of travel by investigators and support staff (e.g., to scientific meetings, investigator meetings, etc.) will be consistent with local guidelines and practices.

#### V. Investigator Commitment

Investigators will be expected to review MSD's Code of Conduct as an appendix to the trial protocol, and in signing the protocol, agree to support these ethical and scientific standards.

### 10.1.2 Financial Disclosure

Financial Disclosure requirements are outlined in the US Food and Drug Administration Regulations, Financial Disclosure by Clinical Investigators (21 CFR Part 54). It is the Sponsor's responsibility to determine, based on these regulations, whether a request for Financial Disclosure information is required. It is the investigator's/subinvestigator's responsibility to comply with any such request.

The investigator/subinvestigator(s) agree, if requested by the Sponsor in accordance with 21 CFR Part 54, to provide his/her financial interests in and/or arrangements with the Sponsor to allow for the submission of complete and accurate certification and disclosure statements. The investigator/subinvestigator(s) further agree to provide this information on a Certification/Disclosure Form, commonly known as a financial disclosure form, provided by the Sponsor. The investigator/subinvestigator(s) also consent to the transmission of this information to the Sponsor in the United States for these purposes. This may involve the transmission of information to countries that do not have laws protecting personal data.

### **10.1.3** Data Protection

Participants will be assigned a unique identifier by the Sponsor. Any participant records or datasets that are transferred to the Sponsor will contain the identifier only; participant names or any information that would make the participant identifiable will not be transferred.

The participant must be informed that his/her personal study-related data will be used by the Sponsor in accordance with local data protection law. The level of disclosure must also be explained to the participant.

The participant must be informed that his/her medical records may be examined by Clinical Quality Assurance auditors or other authorized personnel appointed by the Sponsor, by appropriate IRB/IEC members, and by inspectors from regulatory authorities.

# 10.1.3.1 Confidentiality of Data

By signing this protocol, the investigator affirms to the Sponsor that information furnished to the investigator by the Sponsor will be maintained in confidence, and such information will be divulged to the IRB, IEC, or similar or expert committee; affiliated institution and employees, only under an appropriate understanding of confidentiality with such board or committee, affiliated institution and employees. Data generated by this study will be considered confidential by the investigator, except to the extent that it is included in a publication as provided in the Publications section of this protocol.

# 10.1.3.2 Confidentiality of Participant Records

By signing this protocol, the investigator agrees that the Sponsor (or Sponsor representative), IRB/IEC, or regulatory authority representatives may consult and/or copy study documents to verify worksheet/CRF data. By signing the consent form, the participant agrees to this process. If study documents will be photocopied during the process of verifying worksheet/CRF information, the participant will be identified by unique code only; full names/initials will be masked prior to transmission to the Sponsor.

By signing this protocol, the investigator agrees to treat all participant data used and disclosed in connection with this study in accordance with all applicable privacy laws, rules and regulations.

